8.1. Primary Efficacy Endpoint

[figure not shown]
The primary efficacy endpoint is defined as the proportion of subjects who have a recurrence of uveitis in the study eye within 6 months following treatment. As noted in section 4, all recurrence assessments (including unscheduled visits) on or before the upper limit of the 6 month visit window (Day 208) will be considered. Recurrence is captured on the Recurrence of Uveitis eCRF page and, for the US/FDA, is defined as:

- An increase in the vitreous haze of ≥ 2 steps ([Nussenblatt 1985](#)), compared to baseline or any visit time point prior to Month 6
OR
- A deterioration in visual acuity of at least 15 letters BCVA associated with recurrence of uveitis, compared to baseline or any visit time point prior to Month 6

Any criterion used to define recurrence must be attributable only to non-infectious uveitis. To prevent post-procedural inflammatory reactions from being reported as uveitis recurrences, assessments for recurrence of uveitis will begin after the study Day 7 visit.

The definition of a ≥ 2 step increase in vitreous haze is detailed in the diagram below.

Vitreous Haze: ≥ 2 step increase

* Nussenblatt et al 1985

8.1.1. Primary Analysis

The primary efficacy analysis will be performed on the ITT population at 6 months and will compare the proportion of subjects, in the treatment and control groups, who do not have a recurrence of uveitis in the study eye (as defined above) in the 6 months following Day 1.

The primary efficacy analysis will be conducted after all subjects in the study have completed 6 months of treatment or have discontinued study participation.

The number and percentage of subjects with no recurrence of uveitis in the study eye will be presented by treatment group. A continuity-corrected Chi-square test will be used to assess the statistical significance of a difference between treatment groups in the primary efficacy analysis. Mathematically stated:

$$H_0: 6 \text{ Month Recurrence Free Rate}_{FAI} = 6 \text{ Month Recurrence Free Rate}_{Sham}$$

$$H_1: 6 \text{ Month Recurrence Free Rate}_{FAI} \neq 6 \text{ Month Recurrence Free Rate}_{Sham}$$

The odds ratio for no recurrence (FAI insert/sham) and 95% confidence interval will also be presented.

Although the primary analysis will be performed on both the FDA and ROW definitions of recurrence, no adjustment of type I error will be performed as the FDA and ROW primary efficacy endpoint analyses will be independently evaluated.

The same inferential analysis employing the same methods as for the primary analysis will be performed for the PP population to assess recurrence at Month 6. Additionally, the same analysis will be performed for both the ITT and PP populations to assess recurrence in the exploratory analyses conducted at Months 12 and Month 36. For Month 12, any recurrence at or before the end of the 12 month visit window (Day 388) will be counted. For Month 36, any recurrence at or before the end of the 36 month visit window (Day 1108) will be counted. No adjustment of type I error will be performed as these analyses are considered supportive to the primary analysis.

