14.3.4.1. Primary Efficacy Variable and Analysis

The primary efficacy analysis will be performed on the ITT population at 6 months and will compare the proportion of subjects, in the treatment and control groups, who do not have a recurrence of uveitis in the study eye (as defined in the protocol) in the 6 months following Day 1. To prevent post-procedural inflammatory reactions from being reported as uveitis recurrences, assessments for recurrence of uveitis will begin after study Day 7 visit.

The primary efficacy analysis will be conducted after all subjects in the study have completed 6 months of treatment or have discontinued study participation.

A continuity corrected Chi-square analysis will be used to assess the statistical significance of a difference between study groups in the primary efficacy analysis.

Mathematically stated:

H0: 6 Month Recurrence Free Rate_{FAI} = 6 Month Recurrence Free Rate_{Sham}

H1: 6 Month Recurrence Free Rate_{FAI} ≠ 6 Month Recurrence Free Rate_{Sham}

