4.1. Sample Size

A two group continuity corrected Chi-square test with a 0.05 two-sided significance level will have 89% power to detect the difference between a Sham group recurrence free rate of 0.600 and a FAI treated group recurrence free rate of 0.880 (odds ratio of 0.205) when the sample sizes are 40 and 80, respectively (a total sample size of 120).

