4.2. Randomization, Stratification, and Masking

Subjects will be randomly assigned in a 2:1 ratio to either the FAI insert or sham injection through a central Interactive Voice Response System (IVRS). A blocked randomization will be used and randomization will be stratified on the basis of systemic treatment to control uveitis at the time of study entry. The three strata are: Not receiving systemic treatment, Receiving systemic treatment – corticosteroid therapy, and Receiving systemic treatment – immunosuppressive therapy. Stratification will be achieved dynamically through the IVRS.

To minimize bias, two investigators will be used at each study site. The unmasked treating investigator will inject the FAI insert or perform a sham injection and perform all assessments on study Day 1. The second investigator will serve as the masked assessing investigator and will perform all study assessments after Day 1. Only the unmasked treating investigator will know the assigned study treatment. Study personnel will use every reasonable effort to maintain the study mask.

Unmasking a subject's treatment to the assessing investigator should only be done in emergency situations for reasons of subject safety. In the event that an emergency unmasking is required, the assessing investigator/medically qualified designee has the authority to unmask a subject's treatment using IVRS, or its backup system if IVRS is not functioning. If possible, the assessing investigator/medically qualified designee should contact the PPD medical monitor or designee

before breaking the mask. When the masked treatment code is broken, the date and time of unmasking, name of person doing the unmasking, and the reason for unmasking must be fully documented in the source documentation. Treatment unmasking will also be recorded on the eCRF, including whether the FAI insert was removed and if so, the removal date. In the rare event that the FAI insert is removed, the subject should continue to be followed for safety and recurrence of uveitis through Month 36.

Randomization and unmasking data, for those subjects who were unmasked during the study, will be presented in a listing.

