4.2.1. Masking of Study Team

Prior to the Month 6 database lock, study team members at PPD and pSivida Corp. will be masked to the treatment assignments, with the exception of the PPD randomization team. After the Month 6 database lock, the PPD Biostatistics, Programming and Medical Writing team members and pSivida will become unmasked. The PPD Clinical and Data Management team members will remain masked to subject-level treatment assignments until after the Month 36 database lock.

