Additionally, for missing data due to any reason, sensitivity analyses will be conducted by using multiple imputation (MI) methods. The list of subjects who will have their Month 6 (or 12 or 36) value imputed using MI methods will be determined prior to each database lock. A fully conditional specification (FCS) imputation method will be used to impute missing recurrence values. Five imputations will be performed to obtain five complete data sets. The volume of missing data will be assessed prior to unmasking at Month 6 and the number of imputations may be increased, if necessary. The SAS procedure MI will be used to generate the imputed data sets. The following variables will be included in the imputation model: recurrence, age, gender, treatment group, systemic treatment at study entry (stratification factor), duration of disease (years) in the study eye, number of recurrences in study eye within the 12 months prior to screening, and bilateral uveitis history (yes/no). The imputed datasets will be analyzed by a logistic regression model with recurrence as the dependent term and treatment as the independent term. Using the SAS procedure MIANALYZE, results from the logistic regression analysis of the five imputed data sets will be combined to obtain overall estimates [SAS/STAT User Guide, version 9.3]. Additional details are provided in [Appendix 13.2](#). Note: for this sensitivity analysis, subjects who have not previously experienced a recurrence and who take prohibited medications prior to the time point of interest will have their Month 6 (or 12 or 36) value imputed as a recurrence as described in [Section 8.1.2](#).

The primary efficacy endpoint will be also analyzed with logistic regression with recurrence as the dependent term and treatment as the independent term, and including systemic treatment at study entry (stratification factor) as a covariate.¹

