11.2. Changes Made After Unmasking

Clarifying text was added to section 8.1 to confirm that all recurrences through the end of the 6 month visit window (Day 208) are counted for the primary efficacy variable of recurrence at 6 months. Additional clarifying text was added to section 8.1.1 to confirm the visit windows for which any recurrence will be counted for the analyses at month 12 and 36.

12. References

Retisert Prescribing Information (June 2011).

SAS/STAT User's Guide, version 9.2., SAS Institute, Inc., Cary, North Carolina.

13. Appendices

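### The pooled continuity-corrected primary test runs at about 2.3–3.1% error instead of 5%, gives up about 3 points of power, and ignores the randomisation strata

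*SAP*

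**What the plan says.** SAP 8.1.1 states the primary test: "A continuity-corrected Chi-square test will be used to assess the statistical significance of a difference between treatment groups". Protocol 14.3.4.1 says the same ("A continuity corrected Chi-square analysis will be used to assess the statistical significance of a difference between study groups"), as does the protocol synopsis. Neither brings strata into the test.

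SAP 4.2 describes a 2:1 allocation in which "randomization will be stratified on the basis of systemic treatment to control uveitis at the time of study entry", and names three strata: no systemic treatment, corticosteroid, immunosuppressant.

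The sample size in SAP 4.1 (identical in protocol 14.1) rests on the corrected test: "A two group continuity corrected Chi-square test with a 0.05 two-sided significance level will have 89% power", for "a Sham group recurrence free rate of 0.600" against 0.880 on FAI, with 40 and 80 subjects.

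The only stratum-adjusted test of the treatment effect is a logistic regression in SAP 8.1.3, "including systemic treatment at study entry (stratification factor) as a covariate". It is a sensitivity analysis. The strata also enter the multiple-imputation model, the descriptive subgroups and the time-to-recurrence summaries.

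**The concern.** Two choices each make the primary test more conservative than its nominal level.

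- The continuity correction brings a chi-square close to a conditional exact test. In a trial of this size its true error falls well below 0.05.
- Stratified randomisation balances the arms on the strata. If the strata predict recurrence, a pooled test overstates the variance of the difference and becomes more conservative still.

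Validity is not at stake. What is lost is power that the 120 subjects already provide. That matters because the planning margin may be thinner than it looks. The US SAP drops the anterior-chamber-cell criterion from the definition of recurrence but keeps the protocol's planning rates, and dropping a criterion can only leave or raise the sham recurrence-free rate. Missing Month 6 examinations count as recurrence, and the sample-size text makes no allowance for them. The same corrected test is reused for the per-protocol analysis, Months 12 and 36, and each tipping-point step.

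**Working it through.** **Inputs (SAP 4.1, 4.2).** Two-sided level 0.05; recurrence-free rates p₁ = 0.600 (sham) and p₂ = 0.880 (FAI); d = 0.28; 40 sham and 80 FAI, ratio k = 2; three strata. Stratum sizes and rates are not given and are assumed below.

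**1. The plan's own figure.** Pooled rate p̄ = (0.600 + 2 × 0.880)/3 = 0.787. The uncorrected sham-arm size for 89% power is

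n = [1.96·√(p̄(1−p̄)(1+1/k)) + 1.2265·√(p₁(1−p₁) + p₂(1−p₂)/k)]² / d²
= [1.96 × 0.5017 + 1.2265 × 0.5411]² / 0.0784 = 34.6.

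With the continuity correction,

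n′ = (n/4)·[1 + √(1 + 2(1+1/k)/(n·d))]² = (34.6/4) × [1 + √(1 + 3/9.69)]² = 39.8, so 40 sham and 80 FAI.

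Inverting the formula at n′ = 40 gives 89.2%. Summing over all 41 × 81 possible tables gives an exact 90.4%. The stated 89% reproduces.

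**2. Exact size.** For each table, X² = N(|ad − bc| − c)² / (product of the four margins), with c = N/2 = 60 when corrected (the bracket floored at zero) and c = 0 otherwise. Binomial probabilities are summed over tables with p ≤ 0.05.

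| Common recurrence-free rate | Corrected (planned) | Uncorrected |
|---|---|---|
| 0.60 | 0.031 | 0.050 |
| 0.75 | 0.028 | 0.051 |
| 0.787 | 0.027 | 0.050 |
| 0.88 | 0.023 | 0.046 |

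The range 2.3–3.1% applies between the two planning rates. Outside it, the corrected size is 0.033 at 0.50 (its maximum) and 0.009 at 0.95.

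**3. Exact power.** The first row is the plan; the others are assumed departures from it.

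| Sham vs FAI | Corrected | Uncorrected |
|---|---|---|
| 0.600 vs 0.880 | 0.904 | 0.935 |
| 0.600 vs 0.850 | 0.801 | 0.857 |
| 0.600 vs 0.800 | 0.560 | 0.647 |
| 0.650 vs 0.880 | 0.780 | 0.836 |

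At the planning rates the uncorrected test has power 0.909 with 35 + 70 = 105 subjects, so the correction costs about 120 − 105 = 15 subjects.

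**4. A borderline table.** Take 24/40 sham and 62/80 FAI recurrence-free. Then |ad − bc| = |24 × 18 − 62 × 16| = 560, and the margins multiply to 40 × 80 × 86 × 34 = 9,356,800.
- Uncorrected: 120 × 560² / 9,356,800 = 4.02, p = 0.045.
- Corrected: 120 × 500² / 9,356,800 = 3.21, p = 0.073.

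**5. Using the strata.** 400,000 simulated trials per scenario, marginal rates held at 0.600 and 0.880, common within-stratum odds ratio; 60/30/30 split assumed. Sham patterns are shifted on the logit scale to a marginal 0.600.

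| Assumed sham pattern | Planned test | Pooled uncorrected | CMH uncorrected |
|---|---|---|---|
| Flat | 0.903 | 0.934 | 0.933 |
| 0.75 / 0.50 / 0.40 | 0.912 | 0.942 | 0.949 |
| 0.85 / 0.40 / 0.30 | 0.929 | 0.956 | 0.969 |

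Splits of 66/42/12 and 90/18/12 look the same: CMH gains 2.9 to 4.4 points over the planned test, of which stratification itself supplies 0 to 1.7. Under the null, CMH error stays at about 4.8–5.1%; the planned test's error falls to about 1.2–2.5% under the prognostic patterns.

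**The case against.** The plan contains no error. The test is named consistently, the sample size was calculated for it, and the type I error is protected. Choosing a conservative standard test and powering for it is legitimate. **This stands**, and is why the point concerns efficiency only.

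The full 3 points come from comparison with a test whose exact size slightly exceeds 5% (peak 5.1%). Against Boschloo's test, held at or below 5% (maximum size 4.9%, power 0.922), the gain is 0.922 − 0.904 = 1.8 points. **This stands as a limit on the size of the gain.** The borderline table is also delicate: Fisher's test gives 0.055 and Boschloo's 0.051. It shows that the choice of test can change the verdict, not that the correction hides a clear effect.

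The strata are already used in a pre-specified logistic regression, and their prognostic value is unknown. True, but that regression does not decide the primary conclusion, and CMH gains about 3 points even with flat strata.

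The main remedy may come too late. SAP 4.2.1 says: "After the Month 6 database lock, the PPD Biostatistics, Programming and Medical Writing team members and pSivida will become unmasked", and the SAP has a section headed "Changes Made After Unmasking". **This stands fully:** once data are unmasked, the primary test must not be replaced, and what remains is one supportive output close to the planned logistic regression.

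Changing the test while the sample-size text names the corrected one would leave the two out of step. That is harmless if noted, since 89% then becomes a conservative figure.

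**Conclusion.** The concern holds, as a should-fix efficiency point. At 40 vs 80 the planned test has exact error 2.3–3.1% for common recurrence-free rates between 0.60 and 0.88, and power 0.904 where the uncorrected version has 0.935: about 3 points, or about 15 of 120 subjects. The gap widens to 0.857 − 0.801 = 5.6 points if the true FAI rate is 0.85, and to 0.647 − 0.560 = 8.7 points if it is 0.80 (both assumed).

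These figures are exact and need only the plan's sample sizes and the stated rates. The added gain from stratifying, 0 to 1.7 points, depends on assumed stratum sizes and rates. Neither validity nor the stated 89% is threatened.

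**What to change.** **Before Month 6 data are unmasked:** in SAP 8.1.1, protocol 14.3.4.1 and the protocol synopsis, make the primary test a Cochran-Mantel-Haenszel test over the three strata as randomised, without continuity correction. Report the Mantel-Haenszel odds ratio or a stratified risk difference with its 95% confidence interval. Keep the continuity-corrected chi-square as a sensitivity analysis. Add a line to the sample-size text that 89% was calculated for the corrected test and is conservative for the new one. Check the separate rest-of-world SAP, which shares the protocol, for consistency.

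**Once data are unmasked:** leave the primary test as planned. Report the stratified CMH result beside it at Months 6, 12 and 36, labelled supportive, next to the stratum-adjusted logistic regression already planned.

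**Cost:** wording in those sections, or one added output after unmasking. No new patients or data. The trade-off is an error rate close to 5% (the pooled uncorrected test peaks at 5.1%) instead of well below it.

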8.1.2. Data Imputation

Data for the primary outcome only (recurrence of uveitis) will be imputed using a straightforward method:

- A subject who has not previously experienced a recurrence and does not have the required eye examination data for assessing recurrence at Month 6 (or Month 12 or Month 36 for the Month 12 or 36 analyses, respectively) for any reason will be considered as having a recurrence. If one or more of the required eye examinations, including BCVA and vitreous haze, is not completed at Month 6 (or Month 12 or Month 36), the subject will be considered as having a recurrence. Reasons for missing recurrence data at Month 6 (or 12 or 36) include, but are not limited to: discontinuation from the study prior to visit, visit occurred outside of the visit window, and missed visit.
- A subject who has not previously experienced a recurrence and takes a prohibited systemic concomitant medication as defined in Section 9.10.2 of the protocol any time during the study prior to Month 6 (or Month 12 or Month 36 for the Month 12 or 36 analyses, respectively) will be considered as having a recurrence.
- A subject who has not previously experienced a recurrence and takes a prohibited local concomitant medication in the study eye as defined in Section 9.10.2 of the protocol any time during the study prior to Month 6 (or Month 12 or Month 36 for the Month 12 or 36 analyses, respectively) will be considered as having a recurrence.

Systemic medications administered as part of a gradual dose reduction (tapering) (as described in Section 9.10.1 of the protocol) will not be considered prohibited medications for the analysis of the primary endpoint. For the analysis of the primary endpoint for US/FDA, topical steroids will not be considered a prohibited medication.

The prohibited medication data (based on preferred terms and/or ATC codes) will be reviewed and medications will be categorized as either having a potential impact on the efficacy assessments (consistent with the US/FDA definition of the primary endpoint) or no impact on the efficacy assessments. Only prohibited medications determined to have a potential impact on efficacy assessments will be taken into consideration for data imputation. The list of prohibited medications which will result in an imputed recurrence of uveitis value, for either eye, will be identified prior to each database lock. Note: although local medications are permitted in the fellow eye, in order to ensure consistency in analysis between the study eye and fellow eye, the same list of medications prohibited in the study eye, including local medications, will be considered “prohibited” for the fellow eye for the purposes of recurrence imputation.

A listing of subjects with missing recurrence information at Month 6 (or Month 12 or Month 36 for the Month 12 or 36 analyses, respectively) will be provided. All available recurrence data for these subjects will be included in the listing.

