5.2. Current Treatments for Uveitis

Uveitis is often a chronic disease requiring long-term medical therapy. Currently, medical management of chronic non-infectious uveitis affecting the posterior segment generally includes local administration of corticosteroid (topical, intra- or peri-ocular, intravitreal) and/or systemic administration of steroids or immunosuppressants. Immunosuppressive therapy is used for patients with severe uveitis who are unresponsive to corticosteroid therapy or for patients with severe corticosteroid-induced complications or who are otherwise intolerant of corticosteroid therapy. The goal of therapy is to suppress the inflammation in the back of the eye.

There are disadvantages associated with each of these therapies and their route of administration. All corticosteroid therapy, including systemic, is associated with ocular side effects, including cataract and elevated intraocular pressure (IOP); these side effects are more commonly observed with local therapy. Topical corticosteroid delivery is not effective in the treatment of intermediate or posterior uveitis due to its limited intraocular penetration. Peri-ocular corticosteroid injections may be required frequently and have the additional potential risk for globe perforation, orbital fibrosis, endophthalmitis and ptosis.

Corticosteroids currently approved for the intravitreal treatment of posterior uveitis include Retisert[®], Ozurdex[®], Triescence[®] and Trivaris[®]. Despite the availability of these approved products for intravitreal therapy of uveitis of the posterior segment, systemic corticosteroids are often required to treat uveitis ([MUST group 2011](#)). However, long term use of systemic corticosteroids is associated with significant systemic side effects ([Brunton 2006](#)) and may not be a practical option for many patients.

A product that is relatively simple to administer and delivers corticosteroid locally for an extended period of time may offer significant benefits over existing local and systemic steroid therapies.

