9.10.2. Prohibited Medications

Other than the exceptions described in [Section 9.10.1](#), [Section 9.12](#) or in this section below, the following concomitant medications are not permitted during the study:

- Oral, systemic, injectable, or topical steroids
- Systemic immunosuppressants

Systemic medications or topical steroids administered as part of gradual dose reduction (tapering), as described in [Section 9.10.1](#), are not considered prohibited medications.

Additionally, topical steroids administered as short term standard treatment following an ocular surgical procedure are not considered prohibited medications.

It is advisable for the PI to discuss treatment with the Medical Monitor before administering any prohibited medication unless it is an emergency.

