9.12. Treatment of Recurrences of Uveitis

In the event of a uveitis recurrence in either eye (defined as an “Endpoint”), peri-ocular or intraocular corticosteroid injections, or topical medications should be administered as first line local therapy, in accordance with the protocol. Investigators should consider treatment with topical steroids as first line therapy for a recurrence that involves only an increase in anterior chamber cells with no increase in vitreous opacity. Systemic immunosuppressants or systemic steroids should be used only if local therapy fails.

Subjects who experience a recurrence of uveitis will continue participation in the study. Once the subject’s recurrence is controlled, the treatment regimen (local or systemic therapy) will be ended in a manner that follows the standard of care for ending the specific treatment regimen.

Details of each recurrence and its treatment will be documented in the eCRF.

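### Minor gap in SAP 8.1.2: on the literal text, non-topical rescue of an anterior-chamber-only recurrence in the study eye is neither a US-defined recurrence nor imputed as one

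*SAP*

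**What the plan says.** SAP 8.1.2 takes its medication triggers from the protocol. A subject without an earlier recurrence is imputed as recurrent if he or she "takes a prohibited local concomitant medication in the study eye as defined in Section 9.10.2 of the protocol any time during the study" before the analysis time point. The bullet on systemic drugs uses the same cross-reference.

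Protocol 9.10.2 defines the prohibited set (steroids by oral, systemic, injectable or topical route, and systemic immunosuppressants) only after removing exceptions. Treatment under 9.12 is one of them: "Section 9.12](#) or in this section below, the following concomitant medications are not permitted during the study".

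Protocol 9.12 says that for a recurrence in either eye "peri-ocular or intraocular corticosteroid injections, or topical medications should be administered as first line local therapy", with systemic drugs if local therapy fails. It covers AC-only events expressly: "Investigators should consider treatment with topical steroids as first line therapy for a recurrence that involves only an increase in anterior chamber cells".

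The protocol definition of recurrence (13.1) includes a rise of at least 2 steps in AC cells. The US definition (SAP 8.1, 11.1) has only vitreous haze and visual acuity. SAP 13.3 says the protocol endpoint was deliberately left unrevised.

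SAP 8.1.2 adds one US-specific carve-out: "For the analysis of the primary endpoint for US/FDA, topical steroids will not be considered a prohibited medication". It also describes a list, drawn up before each lock from preferred terms and/or ATC codes: "Only prohibited medications determined to have a potential impact on efficacy assessments will be taken into consideration for data imputation".

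**The concern.** Under the protocol endpoint the 9.12 exception does no harm, because an eye rescued under 9.12 has already met a recurrence criterion. Dropping AC cells from the US endpoint breaks that link. An AC-only event is still a recurrence for treatment purposes but is no longer one for scoring, and its rescue is not a prohibited drug.

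The stake is masking. Protocol 5.2 says of uveitis therapy, including intra- and peri-ocular and systemic treatment: "The goal of therapy is to suppress the inflammation in the back of the eye". A peri-ocular or intraocular steroid, or a systemic drug, given for an AC-only event can hold down the vitreous haze that the US endpoint measures. The eye then reaches Month 6 recurrence-free with help from another drug. The same drug given outside 9.12 would be imputed as a recurrence, so scoring depends on the reason for giving it.

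No planned US sensitivity analysis varies this rule. Those in SAP 8.1.3 change only the handling of missing data, or add the stratification factor to the model, and keep the medication rule.

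**Working it through.** **Tracing the rule for one eye.** Take a study eye with an AC-only rise, rescued by injection under 9.12, with both required Month 6 examinations done and no haze or acuity event by Day 208.

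1. Is there a US-defined recurrence (SAP 8.1)? No: AC cells are not a criterion.
2. Is Month 6 data missing (8.1.2, first bullet)? No.
3. Was a prohibited drug taken (8.1.2, second and third bullets)? No: 9.10.2 excepts 9.12.
4. Does the topical carve-out apply? It is not relevant to an injection or systemic drug.
5. Does the pre-lock list reach this eye? It selects from prohibited medications, which leads back to step 3.

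The eye is scored recurrence-free.

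**The plan's power figure** (SAP 4.1, repeating protocol 14.1). Recurrence-free rates are 0.600 sham and 0.880 FAI, with n = 40 and 80, two-sided 0.05, continuity-corrected chi-square. With d = 0.28 and k = 2, solve n = (n'/4)[1 + √(1 + 2(k+1)/(n'kd))]² for n = 40. This gives n' = 34.82, and uncorrected power at n' is 0.892, which matches the stated 89%. The odds ratio is (0.6/0.4)/(0.88/0.12) = 0.2045, which matches 0.205. Exact enumeration of all 41 × 81 tables gives 0.904, used below.

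**Effect on power.** The documents give no counts of affected eyes, so these are assumptions. Moving s sham and f FAI eyes changes the recurrence rates to 0.40 ± s/40 and 0.12 ± f/80.

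| Eyes moved (sham, FAI) | Planning rates include these eyes; literal reading removes them | Planning rates exclude them; imputing adds them |
|---|---|---|
| 1, 1 | 0.375 vs 0.1075: 0.893 | 0.425 vs 0.1325: 0.915 |
| 2, 1 | 0.350 vs 0.1075: 0.835 | 0.450 vs 0.1325: 0.948 |
| 1, 2 | 0.375 vs 0.0950: 0.927 | 0.425 vs 0.1450: 0.881 |

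**Effect on the test at the design counts.** 0.40 × 40 = 16 and 0.12 × 80 = 9.6, rounded to 10. With x and y events, the statistic is 120(|x(80−y) − y(40−x)| − 60)² / [40 · 80 · (x+y)(120−x−y)]. For 16 and 10: 120 × 820² / (3200 × 26 × 94) = 10.32.

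| Events (sham/40, FAI/80) | Statistic | p | Odds ratio for no recurrence, FAI/sham |
|---|---|---|---|
| 16, 10 | 10.32 | 0.0013 | 4.67 |
| 15, 9 | 9.90 | 0.0017 | 4.73 |
| 14, 9 | 8.24 | 0.0041 | 4.25 |
| 15, 8 | 11.30 | 0.0008 | 5.40 |

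As a limit, remove sham events only. Four lost (12 vs 10) gives 4.35, p = 0.037; five lost (11 vs 10) gives 3.18, p = 0.075. Losing significance would need five of the 16 sham events to be of this kind, with none in the FAI arm.

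**The case against.** The best opposing case is that the SAP means to impute these eyes.

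- The topical carve-out looks redundant if 9.12 rescue is already exempt, so the authors may have thought non-topical rescue would count.
- SAP 8.1.2 restates the taper exception and does not restate 9.12.
- Preferred terms and ATC codes identify the drug, not the reason for giving it, so a listed injected steroid could be imputed whatever the indication. The review is also tied to the US endpoint definition.
- The list counts permitted local drugs in the other eye: "although local medications are permitted in the fellow eye, in order to ensure consistency in analysis between the study eye and fellow eye". Exempting the same rescue in the study eye would sit oddly with that aim.
- Protocol 9.12 labels the triggering recurrence an Endpoint, and an AC-only event is not a US endpoint.

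These points make imputation a plausible intent. They do not settle it. The carve-out still has work to do for topical use outside 9.12. The list is drawn from prohibited medications. The override of a permission is written for the fellow eye only. The per-protocol exclusions (SAP 4.3.2) list systemic treatment for a fellow-eye recurrence separately from imputed endpoints, some sign that 9.12 rescue was not always meant to be imputed.

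Two limits on the concern stand in full. Protocol 9.12 asks investigators to consider topical steroids first for AC-only events, so few eyes should be involved. The Month 6 list is fixed while the study team is masked (SAP 4.2.1), although the sponsor and biostatistics are unmasked for the later locks.

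**Conclusion.** A minor but real gap in the wording of the US primary endpoint derivation. On the text as written, the eyes described are neither recurrences nor imputed. The effect is probably small and its direction unknown: losses mainly in the sham arm shrink the observed difference, and losses mainly in the FAI arm enlarge it. For one or two eyes per arm the conclusion at the design counts does not change. All counts are assumed, and the planning rates are not tied to the US endpoint, since SAP 4.1 repeats the protocol figures.

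Four stronger readings are not supported.

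- A reader might infer that treatment failures are counted as successes. SAP 13.3 records that FDA treats anterior and posterior uveitis as separate indications, so an AC-only event is not in itself a US failure. The issue is possible masking of haze.
- A reader might infer that subjects were in fact scored this way. The pre-lock list is not in the documents, so this cannot be known.
- A reader might include topical rescue. SAP 8.1.2 and 11.1 settle that explicitly.
- A reader might take the rest-of-world (ROW) analysis as a check. It counts every AC-only eye, including those given only topical drugs, so it is a bound and not a substitute.

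**What to change.** State in SAP 8.1.2 that, for the US/FDA endpoint, a recurrence is imputed when a listed peri-ocular or intraocular steroid in the study eye, or a listed systemic steroid or immunosuppressant given for a study-eye event, is started before any US-defined recurrence, even if given under protocol 9.12. Keep the 9.10.1 taper exception and the topical exception.

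Do not extend the rule to systemic treatment given only for the fellow eye. That is a different group, already excluded from the per-protocol population. If it made up 2%, 5% or 10% of otherwise recurrence-free subjects in each arm (assumed), imputing it would lower exact power from 0.904 to 0.876, 0.830 or 0.751.

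Report the opposite handling as a sensitivity analysis at Months 6, 12 and 36. The data exist: SAP 7.1.2 records the reason for each medication, and SAP 8.2 tabulates intra/peri-ocular and systemic adjunctive treatment by arm.

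SAP 11.2 already records changes made after unmasking. If the Month 6 lock has passed, disclose how the pre-lock list treated these eyes, keep that derivation as primary, and label the other post hoc.

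The cost is one sentence, one or two extra table runs, and possibly a few more imputed recurrences. This concerns endpoint scoring only and makes no comment on the rescue rule.
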